7.3.2 Laboratory sample collection and processing

Study staff will collect a nasopharyngeal swab and a venous blood sample from each participant for use in study laboratory procedures. Where permitted by ethics approvals, an oropharyngeal swab will also be obtained to increase the yield of possible respiratory pathogens. In addition, a urine sample will be collected from patients aged ≥ 2 months and

<2 years, and from patients of any age who have pain on micturition, frequent micturition, suprapubic tenderness, or costovertebral angle tenderness. A urine sample will also be collected from HIV-positive inpatients (and HIV-positive outpatients, at sites where resources allow) for uLAM testing. Study staff will prepare the samples and conduct the diagnostic tests described. All other care will be provided by health facility staff.

The FIEBRE study will collect clinical samples for two purposes: for assays that are of immediate clinical benefit to patient care (malaria RDT, HIV testing, serum CrAg, uLAM, blood and urine cultures), and for research purposes. Minimum whole blood volumes needed for tests of immediate benefit to patient care are: approximately 50 uL for malaria and HIV rapid tests; approximately 10 mL for patients aged ≥ 15 years and 4 mL for patients <15 years for blood culture for bacteria and fungi; plus 5 mL for mycobacterial blood culture in patients ≥ 15 years where community HIV prevalence is >1%. In addition, approximately 4 mL of serum (i.e. 8 mL of whole blood), and if possible buffy coat from an EDTA sample, are needed for reference lab testing for infectious diseases (serologies and nucleic acid assays); 250 uL of plasma (i.e. 0.5 mL whole blood) for assays of immune and inflammatory biomarkers; and 2.5 mL of whole blood for additional RNA testing (in a subset of adult participants only; see just below).

For the FIEBRE study, actual blood sampling volumes for young children will be based on body weight up to 7 kg, according to the chart below (Table 1) adapted from various clinical and research guidelines,³² which suggests 2 mL per kg body weight, or 2.5% of estimated total blood volume by body weight, within a 24-hour period as a standard guideline for ill patients. The blood volume to be sampled refers to the total volume that can be drawn for both clinical care and research use. For example, a 2-kg patient could provide a maximum of 5 mL of blood; for a 5-kg patient, 10 mL; and for a 7-kg patient, 14 mL. For the FIEBRE study, weight-based guidelines will be used for all patients ≤ 7 kg.

Table 1. Maximum total blood draw volumes by body weight

Body weight (kg)	Total blood volume (mL)	Max allowable blood volume drawn in 24-hour period* (2.5% of total blood volume in mL)
1	100	2.5
2	200	5

3	240	6
4	320	8
5	400	10
6	480	12
7	560	14

* The total blood volume listed refers to the total blood volume that can be drawn for both clinical care and research procedures.³²

For patients with body weight >7 kg and aged <15 years, the maximum amount of blood drawn will be 15 mL. For patients aged ≥ 15 years, the maximum amount of blood drawn will be 21 mL at sites where HIV prevalence in the general population is ≤1%, and 26 mL at sites where HIV prevalence in the general population is >1% (to allow 5 mL of blood for mycobacterial blood culture). In a randomly selected subset of 180 patients aged ≥15 years at each site, an additional 2.5 mL whole blood will be drawn for storage in PAXgene tubes (containing RNA stabilization solution) for eventual RNA assays; this means that for this subset of patients, the total volume drawn will be 28.5 mL at African sites, and 23.5 mL at Asian sites. (The number of samples collected in PAXgene tubes is limited for budgetary reasons.)

For patients from whom the full volume of blood cannot be obtained for any reason, the available sample will be prioritized as follows: 1) tests performed on-site that are important for clinical management (blood culture, malaria test, HIV test); 2) reference laboratory assays; 3) biomarker assays; 4) aliquots for sample archive and future research use.

If a patient shows clinical signs of severe illness (dehydration, pallor indicating anaemia, hypotension), blood sampling will be discussed with the treating clinician/s and minimized if deemed clinically necessary. In all cases the safety and appropriate care of the patient will be prioritised. For example, adequate volume for blood cultures which will inform clinical care will be prioritized over other study samples.

According to routine practice at each study site, for each participant, a malaria rapid diagnostic test (RDT) or blood smear for routine light microscopy will be performed on site; and an HIV RDT will be performed at sites where community HIV prevalence exceeds 1% in the general adult population (see section 7.6, Specific laboratory assessments). Blood culture

bottles will be inoculated, and bottle weight recorded before and after inoculation to estimate the volume of blood cultured. Blood culture bottles will be incubated at collaborating laboratories for each clinical site. Where obtained, urine samples will be tested with a dipstick for nitrites and leukocyte esterase; samples positive for either will be incubated for culture at collaborating laboratories for each clinical site. Urine samples from HIV-positive patients will be tested for LAM. Bacteria and fungi isolated from clinical specimens will be identified and tested for antimicrobial susceptibility. Any microorganisms isolated will be cryopreserved and shipped to an international reference laboratory for confirmation of identification and antimicrobial susceptibilities; blood samples for each participant will be aliquoted, stored, and shipped to internationally recognised reference laboratories for additional tests (see section 7.6). All personnel will use universal precautions when handling blood samples.

7.3.3 Provision of routine outpatient and inpatient care

Symptoms and signs at the time of enrolment and subsequently will be investigated and managed according to the local standard of care by the health facility staff providing care. Study staff will collect data on symptoms and signs and any treatments given on Day 0. For hospitalized patients, on the day of discharge study staff will record length of stay, condition on discharge, and any treatments administered during hospitalization including antimicrobials. The standard of care for any medical problem that exceeds the capacity of the participating centre is to refer to a higher level of care. As clearly described during the informed consent discussion, treatment and referral will be done at the discretion of the health facility staff.

Results of malaria tests, HIV RDT and CrAg and uLAM point-of-care tests (where performed), blood cultures, and antimicrobial susceptibility profiles of bloodstream and urine isolates will be provided as soon as available to the health facility staff responsible for the management of each patient. Results of serological and molecular tests performed at international reference laboratories will only be available some months after patients are recruited. Some of these tests may diagnose infections that would benefit from appropriate treatment even months later (e.g., serological assays for brucellosis and Q fever). During the informed consent process, study participants will be informed of this possibility, and will be asked to provide their contact details (to be kept in a locked database separate from the study results

databases) so that study staff can notify them of positive reference laboratory results which may benefit from treatment (e.g., brucellosis, Q fever) and if appropriate, prescribe treatment.

Study staff will be available to offer advice to health facility clinicians on interpretation of and appropriate response to test results. If the results of antimicrobial susceptibility testing find evidence of bacterial pathogens that are resistant to all locally available antimicrobials, study staff and investigators will work with local and national health authorities to make available appropriate alternatives.

7.3.4 Scheduling of follow-up visit

All participants will be asked to return to the study site for one follow-up visit 28 days after enrolment. If the visit cannot occur on day 28, another date from day 26 to day 48, inclusive, will be acceptable. For any intervening care-seeking, participants will also be encouraged to return to the study site if feasible. Each participant will be given a card with her/his study identification number and the follow-up study visit date, and on which to record any care or treatment that is received in the interim. At sites where child health records are in routine use, data on interim care will be extracted from these records.

Study staff will attempt to minimize loss-to-follow-up by: telephoning participants/parents/guardians in advance of their scheduled follow-up visit to remind them of the appointment; reimbursing participants' transport costs for study visits; and visiting at home participants who do not keep their follow-up appointment (with appropriate permission obtained at the time of informed consent).

7.4 Study activities for patients at 28-day follow-up visit

7.4.1 Clinical data collection

At each participant's day 28 follow-up visit, study staff will record the clinical outcome of the illness (see sample data collection form, Appendix D). Participants who do not return for the scheduled visit will be followed up at home or by mobile telephone. If the participant reports symptoms at the time of follow-up, s/he will be referred to health facility staff for further investigation and care.

It is recognised that a poor clinical outcome (e.g., permanent disability, death) associated with a health condition may lead to negative and stressful emotions for the participant, those close to her/him, and involved health care providers. In the unfortunate event of a poor clinical outcome, study staff will attempt to collect relevant data in a manner that is sensitive, respectful of the participant's dignity, context-appropriate, and that presents the least inconvenience possible to the participant and her/his family. These ideas, potential scenarios and appropriate methods will be discussed with study staff and health facility staff during pre-study training, and will be based on existing guidance to the extent available.³³

7.4.2 Laboratory sample collection

At each participant's 28-day follow-up visit venous blood will be taken for serology testing. Weight-based guidelines (section 7.3.2) will be used for patients ≤ 7 kg. For patients with body weight >7 kg and aged <5 years, the maximum amount of blood drawn will be 5 mL. At study sites where ethical and regulatory authorities permit, for patients with body weight >7 kg and aged ≥ 5 years and <15 years, the maximum amount of blood drawn will be 10 mL; otherwise the maximum volume for this population will also be 5 mL. For patients aged ≥ 15 years, the maximum amount of blood drawn will be 10 mL. Samples will be aliquoted, stored and shipped to internationally recognised reference laboratories for additional tests (see section 7.6 below).

7.5 Community controls

Interpreting the results of some serological assays and pharyngeal swab assays requires knowledge of background prevalence of infection or colonization in the study population. To address this, 600 community controls (section 11.3 sample size calculations), frequency matched by age, sex, month of enrolment (to address seasonality), and geographical area to the cases, will be selected from the community living in the catchment area of the health facility for each site. No controls will be specifically recruited for the inpatient population, who may come from a wider geographic area. However, an analysis comparing controls with our sample of in-patients who do come from the area from which controls were selected, will be carried out.

7.5.1 Selection and recruitment of community controls

To define the catchment area for outpatients and community controls, existing data and pilot data from each site will be combined to define an area around the study facility in which approximately 80% of outpatients live. Residing within this area will be a selection criterion for FIEBRE outpatients (section 6). Community controls will be recruited within this area, individually matched to participating outpatients.

During each month of the study at each site, half of the outpatients will be selected at random (or by taking every second outpatient in chronological order of presentation). For each of these a community control will be found matched on age (within bands: ≥ 2 to < 6 months, ≥ 6 to < 12 months, ≥ 1 to < 3 years, ≥ 3 to < 5 years, in 5 year bands up to age 24, and in 10 year bands at older ages), sex and place of residence. At sites where the study team's capacity enables them to recruit a larger number of controls, controls will be matched to a larger proportion of enrolled outpatients. For example, if capacity allows, one control will be found for every outpatient; or controls will be found for more than half of the outpatients, e.g. for a random sample of three-quarters of enrolled outpatients (or by selecting every second, third, and fourth outpatient, in chronological order of presentation). This approach will allow us to enhance the precision of estimates for specific primary objective 1 and specific secondary objective 1 (see also section 11.1 below on quantitative outcome measures and analysis).

Community controls will be recruited and enrolled if they, or their parents/guardians, provide informed consent.

7.5.2 Informed consent of community controls

Written informed consent and assent will be obtained for community controls in the same way as described in section 7.2.2 for case/patient participants (Appendices A and B, information sheet and informed consent form for community controls).

7.5.3 Sample collection for community controls

Diagnostic testing will be identical for controls and cases, with three exceptions: blood cultures will not be taken from controls, as the diagnostic yield is likely to be close to zero in this group; convalescent sera will not be collected from controls, as loss-to-follow-up is likely to be so high as to render results unusable; and urine will not be collected from controls.

Venous blood will be drawn from control participants as follows: Weight-based guidelines (section 7.3.2) will be used for controls ≤ 7 kg. For patients with body weight >7 kg and aged <15 years, the maximum amount of blood drawn will be 5 mL. At study sites where ethical and regulatory authorities permit, for controls with body weight >7 kg and aged ≥ 5 years and <15 years, the maximum amount of blood drawn will be 10 mL; otherwise the maximum volume for this population will also be 5 mL. For participants aged ≥ 15 years, the maximum amount of blood drawn will be 10 mL. In a randomly selected subset of 20 controls aged ≥ 15 years at each site, an additional 2.5 mL whole blood will be drawn for storage in PAXgene tubes (containing RNA stabilization solution) for eventual RNA assays; this means that for this subset of control participants, the total volume drawn will be 12.5 mL. (The number of samples collected in PAXgene tubes is limited for budgetary reasons.)

If the malaria RDT is positive for a control participant, antimalarial treatment will be offered according to national guidelines.

7.5.4 Other data collection for community controls, and estimation of population fever incidence and aetiologies

When a control participant provides blood and pharyngeal samples, study staff will collect basic demographic data (age, sex, place of residence, ethnicity). They will be asked if they have a fever and, if they answer yes, their tympanic temperature will be recorded.

In addition, questionnaires will be administered to the community control participants in order to capture more representative data about treatment seeking and medicine (primarily antimicrobial) use. To increase the statistical power of this health care utilisation survey, as for other recent studies that estimate incidence and “burden” of infections,^{21,34} for each control participant, the participant (or head of household or health care decision-maker if the participant is a child) also will be asked about basic demographic information (date of birth or age, and gender) and treatment seeking practices for each household member. This health care utilisation survey will provide an estimate of the period prevalence of fever as well as the proportion of persons with fever in the community who present to the study enrolment sites for care. The fraction of persons with fever presenting to a study site will be used to calculate multipliers to estimate the population-based incidence of fever overall, and the incidence of specific causes of fever in the catchment area of study health care

facilities. This “multiplier” method is well established^{1,22} and is widely used for estimating the incidence of febrile illnesses including but not limited to brucellosis,³⁵ leptospirosis,²¹ and typhoid fever.³⁶ The multiplier method requires an estimate of the total number of cases of fever that present to our study sites. The multiplier method also requires an estimate of the proportion of cases of fever in the population who do not present to the study hospital, which will be obtained through the healthcare utilisation survey among controls. It will also require an estimate of the catchment population for each site, or if that is not possible, for a defined population around each site (which may be smaller than the total catchment area). In the latter case, only health care utilisation data from controls and their household members in the defined population will be used for the estimate of the population incidence of fever in the defined population.

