5 SUMMARY OF STUDY DESIGN

FIEBRE is a study of febrile illness in people aged two months and older residing at one of five sites (three sites in sub-Saharan Africa, two Southeast Asia). Patients who present with fever at the selected facilities will be recruited (Day 0) if they or their guardians/caregivers (in the case of minors) provide written informed consent. Study staff will take a targeted illness and exposure history, and perform a physical examination. Pharyngeal swabs and a venous blood sample will be collected from all participants; a urine sample will be collected from selected participants. Tests for malaria and for HIV (at sites where HIV prevalence exceeds 1% in the general adult population, for patients not already known to be infected), serum cryptococcal antigen (CrAg) and urine lipoarabinomannan (uLAM, a marker of active tuberculosis infection) point-of-care tests (for subsets of patients), and blood cultures will be performed on site; bacteria and fungi isolated from clinical specimens will be identified and tested for antimicrobial susceptibility.

Study patients will be managed by the clinical staff responsible for usual patient care at each study site, according to local standard of care. Results of malaria tests, HIV tests, CrAg and uLAM tests, blood and urine cultures, and antimicrobial susceptibility testing will be provided to the clinical staff as soon as available. Serology and other laboratory tests will be performed at internationally recognised reference laboratories. At Day 28 after enrolment, study patients will be asked to provide a further blood sample for serology and clinical outcome will be evaluated.

Recruitment to the study will be over a 12-month period to ensure that seasonal variations in causes of fever are captured. Background prevalence of specific infections in the study population at each site will be estimated with blood and pharyngeal samples from community controls. In addition, control participants will be surveyed to obtain representative data about treatment seeking and medicines use. By combining data on causes of fever at study sites with the estimate of the proportion of patients with fever seeking care at those facilities, we will estimate the incidence of common infections in the study areas, in order to contribute to efforts to define burden of disease.²¹⁻²⁴ A separate protocol will be prepared and submitted for ethics approval describing in-depth qualitative

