1) To generate data on incidence of specific infections among study participants, and therefore contribute key data on disease burden for some infections that are not counted in current “global burden of disease” estimates;

For an area whose population size is known, a health utilization survey will be used to estimate r , the proportion of fevers for which treatment was sought at a study centre. The total number of cases seen at the study site from the defined population will be multiplied by $1/r$, to obtain the total cases in a year from the defined population. This will be divided by the size of the population to estimate incidence. Incidence of fever caused by specific pathogens will be calculated by multiplying the incidence by the AF for that pathogen.

3) Evaluation of available biomarker assays to assess their performance and potential utility in fever case management in the study areas;

The sensitivity, specificity, and positive and negative predictive value of each biomarker will be estimated.

4) To generate data to support the development of new fever case management algorithms which may be evaluated in future studies;

The association between the presence of pathogens with predefined clinical and other variables will be examined.

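### The survey behind the incidence multiplier draws places in proportion to the attenders they send, so the single care-seeking fraction r does not represent the catchment

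*Protocol*

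**What the plan says.** Section 7.5.1: "Community controls will be recruited within this area, individually matched to participating outpatients". Each month "half of the outpatients will be selected at random (or by taking every second outpatient in chronological order of presentation"), and a control is found for each selected outpatient, matched on age band "and in 10 year bands at older ages), sex and place of residence". Section 7.5 also lists geographical area among the matching factors. Section 6 names only age and season, but refers to 7.5 for the details.

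Section 7.5.4 takes the proportion of community fevers that do or do not reach the study facility from these same people, "which will be obtained through the healthcare utilisation survey among controls", extended to every member of the control's household. Its use is stated there: "The fraction of persons with fever presenting to a study site will be used to calculate multipliers".

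Section 11.1 defines r as "the proportion of fevers for which treatment was sought at a study centre", and continues: "The total number of cases seen at the study site from the defined population will be multiplied by" 1/r. The result is divided by the population size, and pathogen-specific incidence is that figure times the attributable fraction (AF).

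Section 5 states that "control participants will be surveyed to obtain representative data about treatment seeking and medicines use". Section 7.5.4 makes the softer, comparative claim that the data will be more representative.

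**The concern.** Matching controls to patients on residence serves the case-control odds ratio. It does not serve a population survey drawn from the same people. A village that sends twice as many attenders per head contributes twice as many survey households per head. Attendance per head is fever incidence times r, so the sampling fraction depends on a close correlate of the quantity being estimated.

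Any error in r passes unchanged, as a proportion, into overall fever incidence and into every pathogen-specific incidence, which the Protocol offers as input to burden-of-disease estimates. Section 7.5.1 allows extra controls to improve precision for this objective. That narrows the interval but leaves the distortion where it is.

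**Working it through.** The Protocol states no value for r, the multiplier or incidence, so there is no figure to reproduce. All r values below are assumptions.

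**Set-up.** Place a has population N_a, fever incidence f_a and care-seeking fraction r_a. The residence mix of enrolled outpatients is taken to mirror that of attenders.

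- Attenders from place a, and hence matched controls: proportional to N_a f_a r_a.
- True r = Σ N f r / Σ N f.
- Unweighted survey r = Σ N f² r² / Σ N f² r.
- Estimated/true incidence = true r / survey r.
- With equal f: survey r = true r × (1 + CV²), so the incidence ratio is 1/(1 + CV²).

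**One case in full (equal fever; 40% near with r = 0.5, 60% far with r = 0.1).** True r = 0.4×0.5 + 0.6×0.1 = 0.26. Near share of attenders = 0.20/0.26 = 0.769. Survey r = 0.769×0.5 + 0.231×0.1 = 0.408. Ratio = 0.26/0.408 = 0.64, so incidence is 36% too low.

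| Assumed r (two places) | Population shares | Fever in low-r place, relative | True r | Survey r | Incidence ratio |
|---|---|---|---|---|---|
| 0.3 / 0.3 | 50:50 | 1 | 0.300 | 0.300 | 1.00 |
| 0.4 / 0.3 | 50:50 | 1 | 0.350 | 0.357 | 0.98 |
| 0.4 / 0.2 | 50:50 | 1 | 0.300 | 0.333 | 0.90 |
| 0.5 / 0.1 | 40:60 | 1 | 0.260 | 0.408 | 0.64 |
| 0.6 / 0.1 | 30:70 | 1 | 0.250 | 0.460 | 0.54 |
| 0.4 / 0.2 | 50:50 | 1.5 | 0.280 | 0.294 | 0.95 |
| 0.4 / 0.2 | 50:50 | 2 | 0.267 | 0.267 | 1.00 |
| 0.4 / 0.2 | 50:50 | 3 | 0.250 | 0.236 | 1.06 |

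By CV of r, with equal fever: 0.1 gives 1/1.01 = 0.99 (1% low), 0.3 gives 1/1.09 = 0.92 (8% low), and 0.5 gives 1/1.25 = 0.80 (20% low).

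A simulation of the 0.4 / 0.2 case with 600 controls, five persons per household and 10% fever prevalence (the last two assumed) gave a mean survey r of 0.333 against a true 0.300. Including household members does not remove the bias, because they share the control's residence.

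**Check of the remedy (0.4 / 0.2, equal places, 1,000 fevers in each).** Cases seen are 400 and 200. The single survey r gives 600/0.333 = 1,800 fevers against the true 2,000. Summing by stratum gives 400/0.4 + 200/0.2 = 2,000. Weighting surveyed persons by area population / number surveyed returns r = 0.300.

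**The case against.** The strongest reply is that the Protocol never says the fraction is unweighted. Residence is recorded for controls, age and sex for everyone surveyed, and survey weights are the kind of detail an analysis plan may supply. This stands in part, since a later plan could standardise r. But section 11.1 defines one r for the area. The only weighting it states is seasonal, for the AF analysis, and section 5 asserts representativeness outright. Section 7.5.4 asks only for a total population, so the inputs for a correction may not be gathered unless this is settled. Restricting to a defined population moves the boundary but leaves the unequal sampling inside it.

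Three stronger readings are tempting and are not supported:

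- **That incidence is certainly too low.** The direction requires attendance per head to rise with r. The last two rows of the table show the bias vanishing or reversing.
- **That age and sex matching does comparable harm.** Section 7.2.1 enrols by weekly quota in each age-by-setting category, and section 11.2 sets 300 controls per age group. The split at 15 years is therefore fixed near half and half and does not follow attendance. Surveying whole households dilutes the rest.
- **That the sample is selected on the outcome.** Controls are not chosen for having had fever or sought care. They are chosen on a correlate of attendance, which is why weighting can repair the estimate.

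The large scenarios also assume steep contrasts. The catchment is already cut to the area holding about 80% of outpatients, which plausibly narrows them.

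**Conclusion.** The point holds for residence. Followed as written, sections 7.5.1, 7.5.4 and 11.1 give an r that is distorted whenever care-seeking differs between places, apart from coincidental cancellation. Section 5's description of the survey as representative is not justified for unweighted results.

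In the ordinary case, such as r falling with distance while fever rates are similar, incidence is underestimated. The size cannot be learned from the documents. An honest range starts near zero (1% at CV 0.1, 2% for r 0.4 v 0.3), passes 10% for 0.4 v 0.2, and reaches 36% or more only under a fivefold contrast or steeper. A reader might infer a known bias of a third or more, but nothing in the Protocol fixes that figure.

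The effect is confined to secondary objective 1. The AFs and the resistance results do not use r.

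**What to change.** In sections 7.5.4 and 11.1, replace the single r with a residence-standardised one, by either route:

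- weight each surveyed person by area population / number surveyed in that area; or
- compute cases/r within coarse residence strata, sum, and divide by the total population. This needs no population counts by area.

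Standardise also for the two broad age groups where counts allow. Use a variance that allows for household clustering. In section 5, do not call unweighted results representative.

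**Cost.** Recruitment and the questionnaire do not change. Intervals widen somewhat, and with about 600 control households per site the strata must stay coarse to keep enough fevers in each. The first route needs area-level population counts, and section 7.5.4 already allows that even the catchment total may be unobtainable. The second needs cases seen to be classified by place of residence. Section 11.1 already requires cases to be identified as coming from the defined population, so this is a finer version of a task already planned.
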